## **SECTION M: RISKS**

**Describe any expected risks to subjects. Consider physical, psychological, social, political, legal, economic, or other risks that are related to the study.**

The primary risks involved in this study are those associated with alcohol withdrawal, and the use of ZON as monotherapy. The primary risks to the patient are deterioration of symptoms if subjects are receiving placebo.

### Alcohol Withdrawal

Subjects may experience symptoms associated with alcohol withdrawal. Approximately 1.2% (1 out of 85) of subjects in a recent alcohol dependence treatment study (Interdisciplinary Study of Two Novel Anticonvulsants in Alcoholism, 2013), in which anticonvulsants were being evaluated, had experienced withdrawal symptoms severe enough to require in-patient detoxification. Subjects requiring treatment for withdrawal in the present study will be referred for detoxification at other treatment sites and will not be readmitted into this study. The risk of

severe withdrawal is minimized by the requirement that subjects must be sober when they provide informed consent.

Persons drinking at the level required for entry may experience moderate to severe withdrawal symptoms if they stop drinking abruptly or if they attempt to taper their drinking, including shakes or tremors, chills, nausea and/or vomiting, agitation, sleeplessness, seizures, and delirium (disorientation, altered sensorium, and hallucinations).

#### Potential side effects of Zonisamide

The most common adverse reactions associated with ZON administration in seizure patients include: somnolence (17%), dizziness (13%), and anorexia (13%). Less common adverse effects include: agitation (9%), irritability (9%), depression (6%), speech abnormalities (5%), confusion (6%), difficulty with concentration (6%), difficulty with memory (6%), fatigue (8%), insomnia (6%), nausea (9%), and headache (10%). In some patients, ZON can contribute to problems with concentration, attention, memory, mood, thinking, speech, or language. ZON may produce urinary lithiasis [Kubota et al., 2000]. The incidence of this is reported to be 1.9% in clinical trials in the United States and 0.2% in Japanese clinical trials. The risk of urinary stone formation may be higher in dehydrated and bedridden patients.

Acute myopia and secondary angle closure glaucoma have been reported in patients receiving ZON. Symptoms in reported cases have included acute onset of decreased visual acuity and/or ocular pain. Symptoms typically occur within one month after initiating ZON therapy.

Zonisimaide can cause metabolic acidosis, which results in high levels of acid in the body. If untreated, metabolic acidosis can lead to kidney stones or soft bones. Kidney stones can also occur while taking ZON in the absence of metabolic acidosis. The rate of occurrence for kidney stones is 28.7 per 1000 patient-years of exposure in the first six months, 62.6 per 1000 patient-years of exposure between 6 and 12 months, and 24.3 per 1000 patient years of exposure after 12 months of use (Food & Drug Administration (FDA), 2020).

Other rare but potentially life threatening side effects include allergic reactions that may affect different parts of the body, cause blood cell changes such as reduced white blood cells counts, or lead to a serious skin rash such as Stevens-Johnson Syndrome (SJS) or Toxic Epidermal Necrolysis (TEN). SJS and TEN are two forms of the same life-threatening skin disease that cause rash, skin peeling, and sores on the mucous membranes.

Finally, psychotic episodes have occurred in patients being treated with ZON with the risk being higher in younger patients (Miyamoto et al., 2000). One case of ZON-induced systemic lupus erythematosus has been reported in a child being treated with ZON and the anticonvulsant agent ethosuximide (Mutoh et al., 2001). This child improved after discontinuation of ZON. Renal tubular acidosis associated with ZON has been reported (Inoue et al., 2000; Mirza et al., 2011). This problem is reversed with the discontinuation of ZON administration.

#### Risks of MRI

There are risks associated with undergoing MRI assessments for people with contraindications to MRI scans (e.g., those with pacemakers or other metallic implants, with a history of sheet metal work, women who are pregnant, and people with claustrophobia. Additionally, subjects may be at risk if unauthorized metallic items, which can fly into the magnet, are brought into the scan room.

**Risks of phlebotomy**

Risks associated with having blood drawn are slight, but may include: excessive bleeding, fainting or feeling lightheaded, hematoma (blood accumulating under the skin) and infection (a slight risk any time the skin is broken). The likelihood of these risks will be minimized by having blood drawn by a trained phlebotomist, nurse, or physician.

**Risks related to disclosing personal information:**

Subjects may experience discomfort and anxiety when answering questionnaires and when responding to tests evaluating their mood states and alcohol cravings. During assessment, subjects may experience some discomfort or anxiety from discussion of personal information. In addition, subjects may experience some interference with daily activities due to scheduling of assessment and treatment sessions.

Subjects may find questions about their history distressing or uncomfortable. They may feel nervous when answering psychological questions.

**Risk of loss of confidentiality**

The investigator and his staff will take every precaution to maintain subject confidentiality; however, there is always the possibility that confidentiality may be broken.

**Describe the plan to minimize risks. Include in the description the availability of any medical or psychological resources.**

The overriding concern of the investigators is the safety of the subjects who participate in this study. Participants will be informed about all risks and told that they may withdraw from the study at any time and may refuse to complete any treatment procedures. Study personnel will be monitoring the patients' clinical condition carefully and constantly and will withdraw patients from the study if their clinical condition warrants.

In order to minimize risks, patients with prominent suicidal ideation (assessed as part of the clinical interviews, including the MINI, and with the self-monitoring forms) will be excluded. Treatment will be closely monitored by the PI in weekly supervision meetings. The MINI Suicidality interview will be used to measure participants' suicidality scores during the screening session, and will be administered to measure suicidality at every session during clinic visits, and at follow up by phone. A significant increase in depression is defined by scoring at least 10 points higher than baseline on the BDI-II, and getting a total scoring of at least 17. Clinical judgement by the study physician or associated licensed psychologist will be used to decide whether a suicidal potential has developed. The clinical case of any patient showing significant increases in depression symptoms or developing suicidal potential will be reviewed by the PI. These patients will be asked to withdraw from the protocol and given or referred to immediate clinical intervention. Appropriate protective factors and safety plan will be followed based on the attached document, if the patient reports suicidal thoughts with high levels of intent

with a specific plan/access, or regardless of plan. Additionally, all patients will be clearly informed of their right to withdraw from the study at any point.

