#### **A. Questionnaires/Interviews (see below for detailed descriptions for each measure):**

- 1) Demographic Information
- 2) Medical History (including information about prior/concomitant medications)
- 3) Anxiety and Related Disorders Interview Schedule
- 4) MINI Suicidality
- 5) Alcohol Timeline Follow-Back (TLFB)
- 6) Alcohol Dependence Scale (ADS)
- 7) Obsessive Compulsive Drinking Scale (OCDS) and the Alcohol Urge Questionnaire (AUQ)
- 8) Clinical Institute Withdrawal Assessment for Alcohol-Alcohol Revised
- 9) Clinical Global Impression Severity (CGI-S) and Improvement (CGI-I) Scales
- 10) Depression Anxiety Stress Scales (DASS)
- 11) Beliefs about Emotions Scale (BES)
- 12) Multidimensional Experiential Avoidance Questionnaire (MEAQ)
- 13) Anxiety Sensitivity Index (ASI)
- 14) Readiness to Change Questionnaire (RTCQ)
- 15) The Personality Inventory for DSM-5 – Brief Form (PID-5-BF)

- 16) Personality Assessment Inventory – Borderline Features Scale (PAI-BOR)
- 17) Inventory of Statements About Self-Injury (ISAS)

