**III. Alcohol Use Related Assessments**

- A) **Alcohol Dependence Scale (ADS)** - Alcohol dependence will be assessed using the ADS. This 25-item scale has an internal consistency reliability estimate of 0.92 (Skinner & Allen 1982).
- B) **Beck Depression Inventory II (BDI-II)** - BDI II will be used to detect depression in participants. The 21-item assessment encompasses all DSM-based depressive symptoms.

The BDI-II has been found to be reliable among medical samples (and it has demonstrated stability among psychiatric ( $r = 0.92$ ) and student ( $r = 0.93$ ) samples (Beck et al., 1996).

- C) **Alcohol Timeline Follow-Back (TLFB)** - TLFB will be used to estimate participants' daily drinking. In this assessment, participants are presented with a calendar and asked to provide retrospective estimates of their daily alcohol consumption over a specified time period. It takes approximately 25-30 minutes to gather 12 months of data, and approximately 10 minutes to gather 90 days of data. The TLFB has a high test-retest reliability and correlates with other established measures of alcohol use (Sobell & Sobell, 1992).
- D) **Clinical Institute Withdrawal Assessment for Alcohol Scale, Revised (CIWA-A)** - CIWA-A will be used to evaluate the severity of withdrawal symptoms. This 10-item scale, shortened from the 15-item CIWA-A scale, retains significant accuracy when compared to the original CIWA-A ( $r=0.99$ ; Sullivan, Sykora, Schneiderman, Naranjo & Sellers, 1989).
- E) **Obsessive Compulsive Drinking Scale (OCDS)** - OCDS will be used to assess alcohol craving and the urge to drink. The OCDS is a 14-item self-report questionnaire developed based on the Yale-Brown Obsessive Compulsive Scale, an interview-based rating scale. It takes approximately 5-10 minutes to complete. The OCDS is significantly correlated with independent measures of alcohol craving and with the amount of alcohol consumed, and has a positive relationship with independent measures of the severity of alcoholism (Anton, Moak, & Latham, 1995).
- F) **Alcohol Use Questionnaire (AUQ)** - AUQ will be used to assess alcohol craving and the urge to drink. The AUQ is an 8-item self-report questionnaire, in which participants rate their agreement or disagreement to statements on a Likert-type scale. AUQ scores are strongly correlated to the severity of alcohol dependence and to cognitive preoccupation with alcohol, and decline with prolonged abstinence from alcohol (Bohn, Krahn, Staehler, 1995)

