**K. Alcohol Cues Task** - The Alcohol Cues Task entails the presentation of five sets of images, with both neutral and alcohol-related images. These cues will be shown to subjects using a behavioral experiment software called E-Prime. Subjects will be instructed to look at the images on the screen in the MRI scanner. There are five runs of the task. In the beginning of each run, participant will see "Get Ready" on the screen. There are 22 pictures in each run. In each run, participant will see a fixation cross for a varied amount of time from 6000 milliseconds to 14000 milliseconds followed by the presentation of an alcohol image or a neutral image for 4000 milliseconds. In each run there are 2 images with animals in it. Participants are instructed to press a red button on a button box each time they see an animal that is not a human on the screen. The entire task takes approximately 40 minutes to complete.

**Table 1.** *Schedule for assessments and interventions for the Screening Period, Treatment Weeks 1-12, Dose Taper weeks 13 and 14, Follow-Up week 16.*

*Assessments for week 1 occur prior to the start of treatments.*

*Cmeds/AE=Concomitant Medications /Adverse Events, CIWA-AR=Clinical Institute Withdrawal Assessment for Alcohol Use*

Assessment	S C	1	2	3	4	5	6	7	8	9	1 0	1 1	1 2	1 3	14	15	16
Medical /Biological Assessment																	
Medical History	X																X
Birth Control	X	X			X				X				X				
Vitals/Weight	X	X	X	X	X	X	X	X	X	X	X	X	X	X	X	X	
BAC	X	X	X	X	X	X	X	X	X	X	X	X	X	X	X	X	
Pregnancy Test HCG	X	X	X	X	X	X	X	X	X	X	X	X	X	X	X	X	
Urine Drug Screen	X	X			X					X			X				
Urine EtG		X											X				
Blood Lab Tests	X	X		X	X		X		X		X	X	X				
Pill Count			X	X	X	X	X	X	X	X	X	X	X	X		X	
Portland Neurotoxicity Scale		X	X		X		X		X				X				
CMeds/AE	X	X	X	X	X	X	X	X	X	X	X	X	X	X		X	
CIWA-AR	X	X	X		X		X		X				X		X		
Zonisamide										X							
Clinician Interviews																	
ADIS-5	X															X	
MINI Suicidality	X	X	X	X	X	X	X	X	X	X	X	X	X	X	X	X	
TLFB	X	X	X	X	X	X	X	X	X	X	X	X	X	X	X	X	
Questionnaires																	
Demographic	X																
BDI-II		X											X				
ADS	X																
OCDS	X			X					X			X				X	
AUQ	X			X					X			X				X	
CGI-S & CGI-I	X	X	X	X	X	X	X	X	X	X	X	X	X	X	X	X	
DASS	X												X				
BES	X												X				
MEAQ	X												X				

	ASI	X									X			
	RTCQ	X									X			
	PID-5-BF	X									X			
	PAI-BOR	X									X			
	ISAS	X												
	Q-LES-Q	X									X			
	WSAS	X									X			

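### The BDI-II depression rule in Section M has no scheduled data between week 1 (pre-treatment) and week 12

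*Combined protocol and SAP*

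**What the plan says.** The plan to minimize risks in Section M sets the criterion: "A significant increase in depression is defined by scoring at least 10 points higher than baseline on the BDI-II", with a total of at least 17 also required. The consequences follow directly: "The clinical case of any patient showing significant increases in depression symptoms or developing suicidal potential will be reviewed by the PI", and "These patients will be asked to withdraw from the protocol and given or referred to immediate clinical intervention". Clinical judgement is assigned in the same paragraph to whether suicidal potential has developed. The depression criterion itself is left to the score.

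The description of measures in Section L names the instrument for this purpose: "BDI II will be used to detect depression in participants". Its timing is given only in Table 1 ("Schedule for assessments and interventions for the Screening Period, Treatment Weeks 1-12"), where the BDI-II row is marked at weeks 1 and 12 and nowhere else. The table's note says "Assessments for week 1 occur prior to the start of treatments", so the week 1 score is the baseline. The in-clinic screening list includes the DASS but not the BDI-II.

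Section M also has a general safeguard: staff monitor patients' condition and "will withdraw patients from the study if their clinical condition warrants".

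**The concern.** A rule that compares a follow-up score with baseline needs follow-up scores. The schedule supplies one, at week 12, which is also the week in which Section L begins the taper. On scheduled data the rule therefore cannot act during titration or most of maintenance, and those are the periods in which a request to withdraw would still spare the patient drug exposure.

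Section M lists depression among the adverse effects of zonisamide. Section I excludes patients at suicidal risk but does not make current depression an exclusion in itself, so the patient the rule is meant for, whose mood worsens without suicidality, can be enrolled. Until week 12, action for that patient depends on how individual staff judge adverse-event reports and general condition, with no stated cut-off. Similar cases could be handled differently.

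**Working it through.** **1. What is scheduled (Table 1, screening and weeks 1 to 16).** The BDI-II row has a full set of cells and aligns with the header.

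| Measure | Scheduled at | Visits in weeks 2–11 |
|---|---|---|
| BDI-II | weeks 1, 12 | 0 of 10 |
| DASS | screening, week 12 | 0 of 10 |
| Portland Neurotoxicity Scale | weeks 1, 2, 4, 6, 8, 12 | 4 of 10 |
| CGI-S and CGI-I | screening, then every week through treatment | 10 of 10 |
| Adverse events | screening, then every week through treatment | 10 of 10 |
| MINI Suicidality | screening, then every week through treatment | 10 of 10 |

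The DASS does not fill the gap. The measures taken at every visit are not part of the depression definition.

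**2. Could this be a misread table?** The zonisamide level is marked at week 9 in the table but placed at week 8 in the text, so single marks may be one column off. Shifting each BDI-II mark inward by one column gives weeks 2 and 11. Weeks 3 to 10, which is 8 visits, would still be empty.

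**3. Dosing before the first scheduled check**, taking visits on day 1 of each week:

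- Days before the week 12 visit: 11 × 7 = 77.
- Total under the taper text in Section L (300 mg for all of week 12, then three days at 200 mg and three at 100 mg): 77 + 7 + 3 + 3 = 90. Share: 77/90 = 0.856.
- Total if the 13-day taper follows 12 full weeks: 84 + 13 = 97. Share: 77/97 = 0.794.

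**4. Participants with no scheduled post-baseline score.** The Power Analysis cites about 20% dropout before week 12 in the earlier study, not split by arm: 0.20 × 100 = 20. An assumed range of 10% to 30% gives 10 to 30.

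**5. Comparison with the plan's other numeric rules.** The metabolic, renal and liver rules are backed by blood chemistry about every two weeks. The withdrawal rule (CIWA-AR above 10) opens on suspicion at any time, and Table 1 also schedules that scale at weeks 2, 4, 6 and 8. The depression rule has neither interim data nor an instruction to collect it.

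**6. Effect of the fix on the gap.** Now: 12 − 1 = 11 weeks. With checks at weeks 1, 4, 8 and 12 the gaps are 3, 4 and 4, so the longest is 4 weeks. With the second check at week 9 instead, the gaps are 3, 5 and 3, so the longest is 5.

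**7. Possible effect of the fix on power.** Two-sided two-sample t-test, alpha 0.05, effect size 0.74 from the Power Analysis. At 40 per arm this gives 0.905, which reproduces the plan's 0.9. With assumed extra losses in one arm only:

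| Completers per arm | Power |
|---|---|
| 40/39 | 0.901 |
| 40/38 | 0.897 |
| 40/37 | 0.893 |
| 40/36 | 0.889 |
| 40/35 | 0.884 |

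**The case against.** The strongest reply is that the gap is narrow. Suicidality is checked at every session, clinicians rate the CGI and record adverse events at every treatment visit, the PI supervises weekly, a physician is on call at all times, severe drug reactions get a physician's evaluation, and the dose can be reduced. Staff may withdraw a patient on clinical grounds, and nothing forbids an unscheduled BDI-II. Only a BDI-II can apply a BDI-II threshold, so the absence of interim scores does not show that worsening depression would go unnoticed or untreated.

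Much of this stands. Participants are monitored, and the gap concerns only the stated cut-off and only depression without suicidality. The dropout count is also limited: people who have left can no longer be asked to withdraw, so what they lose is a score and a possible referral. No document fixes an interval between checks, so the exact weeks are a matter of judgement.

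The reply does not rescue the rule as written. The plan chose a number for acting on depression, then scheduled almost nothing to compare with it. Section M does not tell staff to give a BDI-II when mood seems to worsen, although its alcohol-withdrawal rule does open on suspicion.

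**Conclusion.** The concern holds and should be fixed. The mismatch between the rule and the schedule is certain from the text and survives a one-column error in the table. The day counts assume visits on the first day of each week, and the dropout figure assumes that the earlier study's rate carries over. The documents give no rate at which participants would meet the threshold, so the number of missed triggers cannot be estimated. The fault is in one safety rule. The schedule gap itself does not affect the efficacy endpoints, their analysis or the sample size.

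**What to change.** - Add the BDI-II to Table 1 at interim visits, at least weeks 4 and 8, and score it at the visit.
- Give it at the first weekly taper visit after early withdrawal. Section L already asks withdrawn participants to return for these visits.
- State in Section M that it is also given whenever worsening mood is suspected.
- Settle when 400 mg begins. The dosing table starts it at week 7, so week 8 falls within maintenance, though before the roughly two weeks that Section L allows for steady state. The text's seven-week titration would start it at week 8; the second check should then be at week 9 or later, and the 5-week gap accepted or another check added.
- State that outcome assessments continue after withdrawal under this rule where the participant agrees. The existing provision for remaining in the study covers stopping medication, whereas this rule asks patients to leave the protocol.

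The cost is a protocol amendment and a few minutes for a 21-item self-report at two existing visits, plus the early-withdrawal and suspicion-triggered administrations. Most questionnaires are already electronic. More checks may produce more withdrawals, possibly unequal between arms. Under the illustration above, 1 to 5 extra losses in one arm cost at most about 0.02 of power (0.905 − 0.884 = 0.021). Bias from unequal losses is the larger risk, which is the reason to continue outcome assessments.
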